4.6. RANDOMISATION

The design for this study includes four centers, with two centers randomly assigned to the treatment “honey” group and the remaining two to the control “no-honey” group.

Individual randomization poses practical limitations due to the rarity of juvenile-onset open-angle glaucoma (JOAG). In this context, such randomization is more feasible and logically advantageous, particularly in terms of coordinating the supply *Kelulut* honey to patients and simplifies distribution of *Kelulut* honey. The *Kelulut* honey is supplied to participants on a monthly basis. During each monthly visit, compliance with the honey

consumption regimen is reviewed, and any potential side effects are systematically monitored and documented. This regular follow-up ensures adherence to the intervention and allows for timely identification of adverse events, thereby enhancing the safety and reliability of the study.

Blood samples for the measurement of serum Interleukin-6 (IL-6) levels will be collected and these samples will then be transported under controlled conditions to the HUSM (Hospital Universiti Sains Malaysia) laboratory for analysis. This ensures a coordinated transportation of blood samples to HUSM laboratory.

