4.10.7. FOLLOW UP

Patients are assessed after a period of 3 months. RNFL thickness and serum IL-6 level will be measured. All these parameters will be measured using the same machine using same techniques. Compliance to the honey supplement will also be tested, by evaluating the diary filled by the patients and the consumed honey packages. Participants who were found to be less than 75 % compliant with the study were excluded from the study.

CHAPTER 5: RESULTS

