9.6. RISK AND BENEFITS TO STUDY PARTICIPANTS

There are no serious adverse effects by the study procedures such as slit lamp examination/ RNFL measurement/venipuncture for serum IL 6 measurement. Dosage of the honey provided to the patient is within the therapeutic dosage. Patient will be periodically for adverse effect during monthly follow up. In case of developing adverse effects to the honey, patients are advised to immediately stop the honey, contact the study doctor and seek immediate treatment from the emergency service at the nearest hospital.

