12.1 PATIENT INFORMATION AND CONSENT FORM

12.2 DATA COLLECTION FORM

12.3 HONEY TREATMENT DIARY

Serial number	
MRN	
Group	

DATA COLLECTION FORM

Supplementary Kelulut Honey Therapy In Juvenile Open-Angle Glaucoma: Effects On IL-6, RNFL And Dry Eye

A. BIODATA OF PATIENT:

Date of birth	
MRN	
Age	
Gender	
Race	

B. SYSTEMIC DISEASES:

[figure not shown]
[figure not shown]
Diabetes mellitus Type I	
Diabetes mellitus Type II	
Hypertension	
Hypercholesterolemia	
Autoimmune disease	
Malignancy	
Tuberculosis	
Systemic lupus erythematosus	
Allergy	
Others	

C. DIAGNOSIS:

	RIGHT EYE		LEFT EYE	
Type of glaucoma	JOAG	POAG	JOAG	POAG
Date of diagnosis				
Onset of disease				
Duration of disease				
Severity of glaucoma	Mild		Mild	
	Moderate		Moderate	
	Severe		Severe	

[figure not shown]
[figure not shown]
D. OCULAR EXAMINATION**PRE-HONEY**

Date of examination:

	RIGHT EYE		LEFT EYE	
Visual acuity	unaided		unaided	
	pinhole		pinhole	
Intraocular pressure	RE			
	LE			
Gonscopy (Shaffer Grading)				
Fundus				
Humphrey visual field test	Pattern			
	MD			
	VFI			
Antiglaucoma eyedrops				
Types of ocular surgery				

POST HONEY

Date of examination:

	RIGHT EYE		LEFT EYE	
Visual acuity	unaided		unaided	
	pinhole		pinhole	
Intraocular pressure	RE			
	LE			
Gonscopy (Shaffer Grading)				
Fundus				
Humphrey visual field test	Pattern			
	MD			
	VFI			
Antiglaucoma eyedrops				
Types of ocular surgery				

E. Investigated parameters

		PRE-HONEY	POST HONEY
Serum IL-6 level (pg/mL)			
Retinal nerve fiber layer thickness (μm)	Mean		
	Superior		
	Inferior		
	Nasal		
	Temporal		
Tear break up time (seconds)			
Schirmer test (mm)			
Glycated haemoglobin HbA1c(%)			

TREATMENT DIARY

Name	
IC	
RN	

HONEY TREATMENT DIARY (to be completed by patient)

DAY	DATE	HONEY USAGE (✓ FOR YES, X FOR NO)	NOTES (SIDE EFFECTS)
1			
2			
3			
4			
5			
6			
7			
8			
9			
10			
11			
12			
13			
14			
15			
16			
17			
18			
19			
20			
21			
22			
23			
24			
25			
26			
27			
28			
29			
30			
31			
32			
33			
34			
35			
36			
37			
38			

39			
40			
41			
42			
43			
44			
45			
46			
47			
48			
49			
50			
51			
52			
53			
54			
55			
56			
57			
58			
59			
60			
61			
62			
63			
64			
65			
66			
67			
68			
69			
70			
71			
72			
73			
74			
75			
76			
77			
78			
79			
80			
81			
82			
83			
84			
85			
86			
87			
88			
89			
90			

MONTHLY SUMMARY TABLE (to be completed by principal investigator)

MONTH	NUMBER OF SACHET CONSUMED	SIDE EFFECTS	COMPLIANCE (%)

1			
2			
3

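### Side-effect fields exist only on the honey-sachet forms, so the plan supplies no control rate against which to read side effects under honey

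*Protocol*

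**What the plan says.** Protocol section 4.6 states that "honey is supplied to participants on a monthly basis". At each of those visits compliance with honey is reviewed and "any potential side effects are systematically monitored and documented". Section 9.6 has a second, incomplete statement: "Patient will be periodically for adverse effect during monthly follow up". It names no arm, but the sentence after it is about the product only: "In case of developing adverse effects to the honey, patients are advised to immediately stop the honey".

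Two forms have somewhere to write a side effect, both in section 12.3. One is headed "HONEY TREATMENT DIARY (to be completed by patient"; it has 90 daily lines, a column for honey use and a column marked "NOTES (SIDE EFFECTS". The other, headed "MONTHLY SUMMARY TABLE (to be completed by principal investigator", has columns for sachets consumed, side effects and percentage compliance. Section 4.7 has the diary ticked when the day's sachet is finished, and gives the control group neither honey nor placebo.

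For both arms the protocol states a baseline assessment and a reassessment at 3 months (4.10.1). Section 4.10.7 gives the content of the latter: "Patients are assessed after a period of 3 months. RNFL thickness and serum IL-6 level will be measured", plus compliance with honey.

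**The concern.** Side-effect recording is attached to honey supply rather than to trial participation. Background symptoms such as a rash, a cough, a stomach upset or irritation from glaucoma drops can occur in either arm over 3 months. If they are written down systematically only where there is a sachet form, the reported honey side effects will mix product effects with background, and nothing in the data will separate the two.

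The design makes this harder to repair later. Whole centres are allocated, two per arm (4.6), so the two control hospitals would have no side-effect form in use at all, and no centre would supply both arms. Patients and the principal investigator know the treatment (4.7), so spontaneous reports cannot be expected to fill the gap evenly. Section 4.6 presents the monthly review as strengthening the safety and reliability of the study, which the recording tools support for one arm only.

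**Working it through.** The plan states no figure on this point, so the check is mainly a comparison of the places where a side effect could be recorded.

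| Place in protocol | What is recorded | Arm | Side-effect item |
|---|---|---|---|
| 4.6, monthly visit | honey supply, compliance, side effects | not named; described with honey supply | yes |
| 9.6, monthly follow-up | adverse effects | not named; next sentence concerns honey | yes, but no form given |
| 12.3, diary | daily honey use, side effects | sachet users, by its layout | yes |
| 12.3, monthly summary | sachets, side effects, compliance | sachet users, by its layout | yes |
| 4.10.1, reassessment at 3 months | IL-6 and RNFL re-measured | both | none |
| 4.10.7, follow-up | RNFL, IL-6, honey compliance | patients in general | none |
| 12.2, Data Collection Form | acuity, pressure, gonioscopy, fundus, visual field, drops, surgery, IL-6, RNFL, TBUT, Schirmer, HbA1c | has a group box, so read as shared | none before or after |
| 9.5, withdrawal | reason for withdrawal | all | only as a reason, tied to the study product |
| Chapter 5, table shells | demographics, IL-6, RNFL, TBUT, Schirmer, HbA1c | both | none |

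The allergy row on the Data Collection Form sits under systemic diseases, so it is medical history and not an event during the study.

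The result is that every side-effect field belongs to a sachet form, and every assessment stated for both arms lacks one.

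Size, using section 4.4:

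- Patients per arm: 24 / (1 − 0.20) = 30, which reproduces the stated 30.
- Space for side effects in the honey arm: 30 × 90 = 2,700 diary lines and 30 × 3 = 90 monthly summary rows. For controls, no form provides any. These figures count space on forms, not questions asked.

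What a one-arm record can say (exact Clopper-Pearson 95% intervals; the event counts are assumptions, since the protocol gives no expected rate):

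- 0 of 30: upper limit 1 − 0.025^(1/30) = 11.6%. With 24 completers: 1 − 0.025^(1/24) = 14.2%.
- 3 of 30 (10%): 2.1% to 26.5%.
- 6 of 30 (20%): 7.7% to 38.6%.

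These intervals treat patients as independent and ignore centre. None of them can be set against a control rate, because the forms do not produce one.

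**The case against.** The case against has four parts.

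- **Silence is not absence.** Section 9.6 places adverse-effect checks at a monthly follow-up without limiting them to an arm. Section 4.5 uses the honey diary to police honey consumption, and controls are barred from honey too, so a diary with a yes/no column could in principle be given to them. The flow chart in Chapter 6, where a schedule by arm might appear, is not shown in the text available. A reader might infer that controls are never asked about adverse events; the protocol does not say that. What stands is that, even if controls attend monthly, the only fields for an answer are on forms about sachets.
- **Participant protection is the stated purpose.** Section 4.6 speaks of adherence and early detection of adverse events, and no objective, hypothesis or table shell compares side-effect rates between arms. This is correct, and it rules out claiming that the trial would report a false excess. It does not remove the difficulty of interpreting the honey-arm counts.
- **Some safety-relevant data are balanced.** HbA1c is a stated comparison between arms, and TBUT, Schirmer, pressure and acuity are taken in both. This also stands: the gap concerns side-effect reports only.
- **It could be left to the analysis plan.** This does not stand. What is asked, of whom and on which form is settled by the protocol and its appended forms, and no analysis can recover what was not collected.

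**Conclusion.** The point holds in a limited form. As written, the plan provides for systematic side-effect recording under honey only and leaves unclear whether controls are asked at all. It would give a rate for 30 honey patients with no counterpart in 30 controls. The efficacy endpoints are not affected.

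The conclusion assumes that the diary and summary go to sachet users, as their layout suggests, and that the Data Collection Form is used in both arms, as its group box suggests. If the missing flow chart gives controls a monthly adverse-event enquiry, the gap narrows to the lack of a common form.

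It is tempting to go further and put a p-value on a spurious difference, taking the same background rate in both arms with full capture in one and none in the other. The documents do not support this. The rate and the all-or-nothing capture would be invented, no such test is planned, and an individual-level test would ignore that whole centres are allocated.

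**What to change.** 1. Add one adverse-event item (event, date, severity, action taken) to the Data Collection Form, in identical wording, for both arms at the 3-month visit.
2. State in sections 4.6 and 9.6 whether the monthly side-effect review applies to both arms. If controls are seen monthly, ask them the same question. Extra contacts at months 1 and 2 solely for this purpose (30 controls × 2 = 60) are optional.
3. Report side effects by arm from the common form, with the diary as supporting information for the honey arm. Present them descriptively only, because treatment is open and arm is confounded with centre.

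The cost is one row on an existing form and a little more site work; the 3-month item needs no extra visit. It should start at all four centres together, so that both arms are asked in the same way from the same date. Some difference in reporting between arms will remain because treatment is open; the common item gives a control rate but does not make the comparison unbiased.

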4.7. HONEY SUPPLEMENT

The honey used in this study is Brainey Madu Kelulut, harvested from *Heterotrigona Itama*. It will be supplied for a total of three months after the recruitment and completion of initial examination and blood sampling. The participants in the ‘no honey’ group did not receive any placebo. Patient in the ‘no-honey’ group is prohibited from consuming products that is based on honey Kelulut or other honey-based products throughout the study period. The control group will consist of matched JOAG patients receiving standard treatment without honey.

Both the patients and the Principal Investigator will not be blinded by the modality of treatment.

Participants were instructed regarding the consumption of the honey by the Principal Investigator. The honey will be supplied in the form of sachet, dosage of 30g per sachet per day for 3 months. The participants are advised to consume the honey at least 30 minutes prior to meals or other medications to avoid any interactions. Participants are also advised not to mix or dilute the honey using other solutions or food products. Participants are also prohibited from consuming other honey-based products throughout

the duration of the study. Those who develop any allergic reaction such as rashes, shortness of breath, wheezing, dysphagia or anaphylactic reactions are advised to immediately discontinue the product and seek immediate treatment from the nearest Emergency Department and contact the Principal Investigator regarding the side effects.

The principal investigator will also advise the patients regarding the compliance to treatment. The compliance will be monitored via a printed diary that will be given upon enrolment. Patients are required to tick on the diary upon completion of the honey sachets daily.

4.8. DEFINITION OF TERMS

Juvenile open angle glaucoma

Juvenile-onset open-angle glaucoma (JOAG) is a subset of primary open-angle glaucoma that is diagnosed before 40 years of age. *Myocilin* gene mutations are the most commonly associated. JOAG is characterized by high intraocular pressures (IOP) elevation in intraocular pressure with large fluctuations, faster progression and severity of visual field loss compared to adult POAG.

Interleukin-6

IL-6 belongs to the class of four-helical cytokines. The cytokine can be synthesized and secreted by many cells. It acts via a cell surface-expressed interleukin-6 receptor, which is not signaling competent. This receptor, when complexed with interleukin-6, associates with the signaling receptor glycoprotein 130 kDa (gp130), which becomes dimerized and initiates intracellular signaling via the Janus kinase/signal transducer and activator

of transcription and rat sarcoma proto oncogene/mitogen-activated protein kinase/phosphoinositide-3 kinase pathways.

Retinal nerve fiber layer

The retinal nerve fiber layer (RNFL) or nerve fiber layer, stratum opticum, is formed by the expansion of the fibers of the optic nerve; it is thickest near the optic disc, gradually diminishing toward the ora serrata. As the nerve fibers pass through the lamina cribrosa sclerae they lose their medullary sheaths and are continued onward through the choroid and retina as simple axis-cylinders. Upon reaching the internal surface of the retina they radiate from their point of entrance over this surface grouped in bundles, and in many places arranged in plexuses.

Honey Kelulut

Stingless bee honey (Kelulut) is a tropical rainforest honey produced by tropical Meliponini bee species, bees are from genus *Trigona*. stingless bees (*Meliponini* sp.) or *lebah Kelulut* which do not have stingers, build nests in already existing cavities or hollowed out areas of trees, buildings and hives. The major composition of stingless bee honey includes sugars (fructose and glucose) with nearly zero hydroxymethylfurfural (HMF). It also contains small amounts of other compounds, such as organic acids, phenolic compounds (eg., phenolic acids and flavonoids), proteins, amino acids (eg., phenylalanine, alanine, tyrosine, valine, acetate and trigonelline), enzymes, vitamins and minerals.

4.9. STUDY INSTRUMENTS

4.9.1. SLITLAMP BIOMICROSCOPY

Slit lamp biomicroscope (Topcon Corp, Japan) was used for ocular examination. It is used for assessment of the patients' eye through binocular, stereoscopic magnified views of the anterior segment and posterior segment. Posterior segment examination was conducted with the aid of + 78 or +90 Diopter lens.

4.9.2. GOLDMAN APPLANATION TONOMETER (HAAG STREIT, GERMANY)

Goldman applanation tonometer (Haag Streit, Germany) has been regard as a gold standard to measure intraocular pressure (IOP), based on Imbert-Fick principle.

4.9.3. GOLDMAN GONIOSCOPE

The status of angle structure in the anterior segment of the eye was determined by using single mirror Goldman gonioscopy lens.

4.9.4. HUMPHREY VISUAL FIELD ANALYSER II MODEL 750

It is an automated, static, computerized perimetry machine used as the gold standard perimetry to assess patients' visual field. Swedish Interactive Threshold Algorithm Standard (SITA-STANDARD) with test pattern 10-2 or 24-2 full threshold was used as strategy in assessment of visual field.

4.9.5. ELISA KIT

The BioLegend LEGEND MAX™ Human IL-6 ELISA Kit is a Sandwich Enzyme Linked Immunosorbent Assay (ELISA) with a 96-well strip plate that is precoated with a rat monoclonal anti-human IL-6 antibody. The detection antibody is a biotinylated rat monoclonal anti-human IL-6 antibody. This kit is specifically designed for the accurate

quantitation of human IL-6 from cell culture supernatant, serum, plasma, and other biological fluids. This kit is analytically validated with ready-to-use reagents.

4.9.6. OPTICAL COHERENCE TOMOGRAPHY Cirrus HD-OCT 500

(Carl Zeiss Meditec, Germany)

OCT is a noninvasive in vivo cross-sectional imaging technology using low-coherence interferometry. OCT is the optical analogue of ultrasound imaging; it generates high-resolution cross-sectional 2D images of internal tissue microstructures. Specifically pertaining to glaucoma, OCT enables the objective quantitative evaluation of critical neural structures, including the RNFL, the optic nerve head (ONH), and the macula. By comparing these measurements with established normative databases, clinicians can determine whether structures are borderline or outside normal limits, improving detection of disease and its progression.

The eyes are dilated with Gutt Tropicamide 1% and Gutt Phenylephrine 5% before recording the images. Internal fixation was chosen (subject fixation with the eye being studied because of better reproducibility). The average thickness for each composite scan was calculated by taking the arithmetic mean of the 100 data points. In addition, the peripapillary RNFL thickness was divided into four quadrants defined as superior (46 to 135 degrees), nasal (136 to 225 degrees), inferior (226 to 315 degrees), and temporal (316 to 45 degrees).

4.10. DATA COLLECTION AND ANALYSIS

4.10.1. PATIENT RECRUITMENT

The study will be conducted after obtaining approval from the Universiti Sains Malaysia Ethical Committee. Patient from the Department of Ophthalmology Hospital Universiti Sains Malaysia (HUSM), Department of Ophthalmology Hospital Raja Perempuan Zainab II (HRPZ II), Department of Ophthalmology Hospital Sultanah Nur Zahirah (HSNZ) and Department of Ophthalmology Hospital Sultan Ismail Petra (HSIP) will be selected according to our inclusion and exclusion criteria. Participants who fulfilled the selection criteria are identified and provided with the information sheet regarding the study. Written informed consent is obtained from all participants or legal guardian.

The eye with the better visual acuity will be selected to standardize the examination. A comprehensive ophthalmic assessment is done which includes visual acuity, Schirmer test, Tear break-up time (TBUT), intraocular pressure measurement by Goldmann applanation tonometry, slitlamp and fundus examination and gonioscopy using Goldmann three mirror contact lens. OCT macula and RNFL thickness measurement using optical coherence tomography is done after pupillary dilatation by some identified single-blinded trained personnel.

Blood sampling will be taken from all participants, serum separated, stored and transported to HUSM Laboratory and assayed. Quantification of cytokine IL-6 performed using IL-6 enzyme-linked immunosorbent assay (ELISA) kit. The participants were randomized into either ‘honey’ or ‘non-honey’ groups. The honey used in this study is Brainer Madu Kelulut, harvested from *Heterotrigona Itama* supplied for a total of three months after the recruitment and completion of initial examination and

blood sampling. The participants in the ‘no honey’ group did not receive any placebo. After 3 months of honey supplement therapy, participants in both groups were reassessed during follow-up. The mean serum IL-6 and RNFL thickness were re-measured, using the same OCT machine and IL-6 ELISA test kit. Participants who were not compliant to the honey supplement were excluded from the study.

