4.3. SAMPLING METHOD

Sampling method

1. All JOAG patients that fulfilled selection criteria
2. Patients who are treated at Ophthalmology Clinic HUSM, HPRZ II, HSNZ and HSIP from February 2026 – November 2026.

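### Section 4.6 randomises centres but 4.10.1 says participants are randomised after baseline; with open-label centre allocation and no concealment step, approach, entry and consent can depend on the arm

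*Protocol*

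**What the plan says.** Four sections of the protocol describe how a patient reaches an arm.

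- **4.6 Randomisation:** "The design for this study includes four centers, with two centers randomly assigned to the treatment" honey group and the other two to control. It sets individual randomisation aside because the disease is rare and because honey is easier to supply this way.
- **4.10.1 Patient recruitment:** after describing selection, written consent, the eye examination, OCT and blood sampling, it says "The participants were randomized into either" a honey or a non-honey group.
- **4.7 Honey supplement:** "The control group will consist of matched JOAG patients receiving standard treatment without honey". No matching variables are named.
- **4.3 Sampling method:** "All JOAG patients that fulfilled selection criteria".

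On blinding, 4.7 says "Both the patients and the Principal Investigator will not be blinded by the modality of treatment", and controls receive no placebo. Section 4.10.1 states that OCT personnel are single-blinded. Section 4.10.2 states that the staff who collect blood and the laboratory staff who process IL-6 are blinded. No blinding is stated for visual acuity, Schirmer test, TBUT, intraocular pressure, slit lamp or gonioscopy.

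Consent is individual: "Written informed consent is obtained from all participants or legal guardian". Entry under 4.5 requires patients to comply with conventional treatment and to have reached target pressure; neither criterion has a threshold. No section describes allocation concealment or says when the centres are drawn.

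**The concern.** The order of allocation and enrolment decides whether randomisation protects the comparison. If patients are randomised individually after consent and baseline, nobody can choose whom to enrol by arm. If hospitals are randomised and the result is known there, staff can approach and judge patients, and patients can agree or decline, knowing what they will get. The protocol describes both arrangements, and adds a control group that is apparently selected by matching.

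At stake is who is in each arm. If the honey hospitals enrol a different kind of patient from the control hospitals, the contrast mixes selection with any honey effect, and this cannot be repaired once recruitment is over. The problem is separate from allowing for clustering in the analysis and from blinding of outcome assessors: solving either would leave it untouched.

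**Working it through.** No stated figure produces this point, so the main check is a comparison of the text.

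**1. Unit and timing of allocation.**

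| Section | Unit | Place in sequence |
|---|---|---|
| 4.6 | Hospital (4; 2 per arm) | Not stated |
| 4.10.1 | Participant | Sentence follows consent, examination, OCT and blood |
| 4.7 | Matched controls, variables not given | Not stated |
| 4.3 | All eligible patients, no selection | Not applicable |

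4.6 and 4.10.1 disagree on the unit. 4.7 and 4.3 disagree on whether controls are selected.

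**2. When the arm becomes knowable under 4.6.** Each hospital has one arm, and honey is handed out there monthly without a placebo. Even if the draw came late, the arm of every later patient at that hospital is known once the first is allocated. Section 4.3 gives a window of February to November 2026, so entry is probably spread over time.

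**3. Steps open to influence.** These are the approach to patients, the two entry criteria without thresholds, consent, and the assessments with no stated blinding. Schirmer and TBUT are outcomes of specific objective 3, and visual acuity determines which eye is studied (4.10.1). OCT, blood collection and the IL-6 assay are stated to be blinded. Blinding those measurements does not change who was enrolled.

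**4. What the planned analysis removes.** Section 4.10.6 plans repeated-measures ANOVA. With two arms and two times, the time-by-group term compares mean changes. Suppose honey has no effect, and let D0 and D1 be the between-arm differences at baseline and at 3 months. The term then estimates D1 − D0.
- Stable difference: D1 = D0, so the term is 0 and the selection effect cancels.
- Difference that alters the trajectory: D1 ≠ D0, and the term is not 0.

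**5. Consequence if some shift survives (assumed values).** Section 4.4 starts from 24 and treats it as a per-group figure: 24/(1 − 0.20) = 30, which reproduces its 30 per group. The 24 itself cannot be reproduced, because no effect size, SD or correlation is given. Suppose a spurious difference of s SD remains in the quantity compared, with patients treated as independent. A two-sided 5% test with n per arm then rejects with probability Φ(s/√(2/n) − 1.96) + Φ(−s/√(2/n) − 1.96). For s = 0.50 and n = 24, √(2/24) = 0.289 and 0.50/0.289 = 1.73, which gives 41.0%.

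| s (assumed) | n = 24 | n = 30 |
|---|---|---|
| 0 | 5% | 5% |
| 0.25 | 13.9% | 16.2% |
| 0.50 | 41.0% | 49.1% |
| 0.75 | 73.8% | 82.8% |

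This shows how sensitive a trial of this size is to a surviving shift. It does not estimate the shift here.

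**The case against.** Open-label allocation by centre is a declared choice with a stated reason. The randomisation sentence in 4.10.1 also comes after the mention of the ELISA quantification, so that paragraph is not a strict chronology and the sentence may only be loose wording for group assignment. That is fair: it shows ambiguity about the unit, not a firm plan to randomise after baseline. The ambiguity still has to be resolved, and the choice of centre allocation does not supply concealment.

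A reader might infer four stronger things that the documents do not support.

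- **Centres are drawn before anyone is recruited.** The supply rationale makes this plausible, but no timing is stated. The Chapter 6 flow chart, which might show the order, was not visible in the text available to me.
- **Every baseline measurement is made with the arm known.** 4.10.1 and 4.10.2 state blinding for OCT, blood collection and the IL-6 assay. It is fair to ask how on-site staff stay blinded when the whole hospital has one arm, but a central assay can be blinded if labels hide the centre.
- **Controls are offered only blood tests and a honey ban.** 4.10.1 gives all participants a comprehensive eye examination and OCT. Section 9.10 gives them a leaflet, no cost for taking part and, subject to a grant, an honorarium. The offers still differ by the honey itself.
- **Regression to the mean favours honey by a known amount.** If the honey arm were selected to be d SD higher at baseline and the pre-post correlation were r, the spurious difference in change would be (1 − r)d. With assumed d = 0.3, that is (1 − 0.5) × 0.3 = 0.15 SD or (1 − 0.7) × 0.3 = 0.09 SD. But this needs selection on the observed IL-6 value, which is measured only after consent, and nothing implies that the honey arm would start higher. Neither the size nor the direction carries over to this trial.

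**Conclusion.** The point holds in two parts. The contradiction is certain from the text: 4.6 and 4.10.1 differ on the unit of allocation, and 4.7 and 4.3 on how controls are obtained. The recruitment risk follows if 4.6 is the scheme in force. It rests on one arm per hospital, an open-label product, entry criteria without thresholds and no described concealment.

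The size and direction of any bias are unknown. Stable differences between arms cancel in the time-by-group analysis; differences that alter the trajectory over 3 months do not. The rejection rates above depend entirely on assumed shifts. The contradiction must be resolved before recruitment. The protection of recruitment should be added at the same time, because selection cannot be undone afterwards.

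**What to change.** 1. Reconcile 4.6, 4.7 and 4.10.1 so that they state one unit and one timing of allocation. If centres are the unit, correct the sentence in 4.10.1.
2. Before the centre draw is made or disclosed, have each of the four clinics lock a list of patients meeting 4.5 from its existing follow-up records. Approach everyone on the list. Log and flag patients identified later rather than barring them, since the disease is rare and 60 are needed.
3. Use the same information sheet in both arms; the appendix lists a single form, so this may only need confirming. Where practical, obtain consent and baseline for listed patients before the centre's arm is disclosed. This should stay optional, because early baselines would age while the rest are completed.
4. Delete the word matched from 4.7, or define it and reconcile it with 4.3.
5. Report the numbers listed, approached and consented by centre.

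The cost is protocol wording, one list exercise per clinic, and a short delay before the draw and the first honey supply. Locked lists reduce differential consent but do not remove it.
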